10. STATISTICAL CONSIDERATIONS

It is known that tumor pathologic variables, such as invasive ductal carcinoma, high tumor grade and high proliferative activity, are associated with a better response to neoadjuvant treatment. It is also known that triple-receptor negative and HER2 positive tumors respond best to cytotoxic and Herceptin-based regimens, respectively. To estimate the predictive value of these parameters as well as newly acquired hemoglobin parameters from US-guided NIR system, we have developed a logistic regression model which can be used to describe the relationship of several predictor variables X_1, X_2, \dots, X_k to a dichotomous response variable Y , where Y is coded as 1 (responder) or 0 (non-responder) for its two possible categories. We also assess the overall quality of the prediction models through the ROC curves and the area under ROC (AUC). For this purpose, all parameters will be inputted to the prediction model to estimate the predict power on final pathological response. Once the model is validated from the new patient data, it can serve as a guideline for predicting patient response to neoadjuvant treatment.

10.1. Sample Size Calculations

For triple receptor negative breast cancers, recent studies have shown that 40% of the patients achieved pathologic complete response [25]. For Her2 positive breast cancers, recent studies have demonstrated that new anti-cancer regimens trastuzumab (Herceptin) plus lapatinib (Tykerb), or with trastuzumab plus pertuzumab (Perjeta) have resulted in a statistically significantly larger number of patients achieving pathologic complete response [25]. From our pilot study, we have observed a 25% change in total hemoglobin level when compared to pre-treatment baseline (%tHb) between the responder (Miller-Payne grades 4-5) and non-responders (Miller-Payne grades 1-3) at the end of cycle one. However, no statistical test was performed because of the small sample size ($n=5$) for this subgroup. Based on our earlier pilot data of response at end of cycle 1, $n=5$, the estimated sample size needed at significance level of $\alpha = 0.01$ (power 0.99) using difference in mean values and pooled standard deviations of two responder groups obtained from the pilot data of five patients at the end of cycle 1 suggests that 18 patients are required for the Her2 positive group in the new study. We observed an even greater difference of 34.1% in total hemoglobin level when compared to baseline between the two responder groups for triple receptor negative patients at the end of cycle 3. Again, no statistical test was performed because of the small sample size ($n=6$). The estimated sample size needed at significance level of $\alpha = 0.01$ (power 0.99) using difference in mean values and pooled standard deviations of two responder groups obtained from these 6 patients at the end of cycle 3, suggests that 19 patients are required for the triple receptor negative group in the new study. MINITAB two sample t-test was used for calculations.

For ER+ and Her2- patients, recent studies have shown that a pathological complete response is rarely achieved by neoadjuvant chemotherapy. At current practice, most of the patients were treated by hormone therapy which is a much more prolonged treatment than neoadjuvant chemotherapy. We do not plan to immediately recruit patients who will be treated by hormone therapy. In our pilot study, we had a total of 22 patients with ER+ and HER2- cancers and have obtained statistical significance based on tHb difference between responder and non-responder groups at the pre-treatment. We also obtained statistical significance based on %tHb at the end of cycle 1. The estimated sample size needed at

significance level of $\alpha = 0.01$ (power 0.99) using difference in mean values and pooled standard deviations of two responder groups at pre-treatment and end of the cycle 1, suggests that 12 patients are required for this group of patient in the new study. Again, MINITAB two sample t-test was used for calculations.

Based on our past experience, about 20% of the patients may either go to early surgery or drop the study due to side effects of treatment. With the 60 planned patients, we expect to have approximately 50 patients who will complete the study. Based on the patient pool at Washington University, we expect ~18 HER2 positive patients, ~19 triple receptor negative patients in the next two years of the award. The rest will be ER+ and HER- patients.

The adequate sample size of HER2 positive patients and triple receptor negative patients will allow us to evaluate the observation that the best time windows for predicting early response based on %tHb changes is within the first cycle for HER+ patients, and the best window for predicting early response is within the first three cycles for triple receptor negative patients. The new data that will be obtained at the end of day 7 may offer new insight into early tumor responses of these two major treatment groups.

Although the Taxol-based and Herceptin-based regimens have an important place in the treatment of breast cancer, many alternatives or new anti-cancer regimens are equally interesting and acceptable. We anticipate that a small population of patients of the proposed large patient cohort will be treated with novel regimens as these new treatments become available for clinical trials, and the results for these regimens can be used as pilot data for the efficacy of the new regimens.

For the exploratory cohort, we plan to enroll 10 patients.

In summary, sixty eligible patients will be enrolled and ~50 patients are expected to complete the study. Based on the patient pool at Washington University, we expect to recruit ~18 HER2-positive patients, ~19 triple negative patients, and the rest may be ER-positive and HER2-negative patients.

We will thereby begin to benchmark the optical signature of neoadjuvant treatment response of subsets of breast cancer based on molecular phenotype.

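### Section 10.1 does not say whether 18 (HER2-positive) and 19 (triple-negative) are per responder group or in total; if per group, as the odd 19 suggests, the subtype t-test has power of about 0.75, not 0.99

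*Combined protocol and SAP*

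**What the plan says.** Section 10.1 (Sample Size Calculations) compares responders (Miller-Payne grades 4-5) with non-responders (grades 1-3) within each molecular subtype. All three calculations use a two-sample t-test at alpha 0.01 and power 0.99, with the mean difference and pooled SD taken from the pilot.

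- **HER2-positive:** 18 patients required. The pilot had five such patients, and the authors write that "we have observed a 25% change in total hemoglobin level when compared to pre-treatment baseline (%tHb) between the responder" and non-responder groups at the end of cycle 1.
- **Triple-negative:** the pilot had six patients. "We observed an even greater difference of 34.1% in total hemoglobin level when compared to baseline between the two responder groups" at the end of cycle 3. The calculation "suggests that 19 patients are required for the triple receptor negative group in the new study. MINITAB two sample t-test was used for calculations".
- **ER-positive/HER2-negative:** the calculation "suggests that 12 patients are required for this group of patient in the new study". Neither the difference nor the SD is given.

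The closing summary of 10.1 turns two of these requirements into counts for the whole subtype: "we expect to recruit ~18 HER2-positive patients, ~19 triple negative patients". ER-positive/HER2-negative patients make up the remainder. Enrolment is 60, losses are put at about 20%, and about 50 patients are expected to complete.

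No pooled SD, sidedness or responder:non-responder split is given. The section does not say whether 18, 19 and 12 are per responder group or subtype totals.

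**The concern.** The usual sample size formula for a two-sample t-test is written in patients per group, and two equal groups always give an even total. A requirement of 19 is therefore natural as a per-group size, but as a total it needs an unequal split, and none is stated. The likeliest explanation is that per-group sizes were carried forward as subtype totals.

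If so, HER2-positive and triple-negative disease would need 2 × 18 = 36 and 2 × 19 = 38 patients for the stated power, twice what is planned. The chance of missing a difference as large as the assumed one would be about one in four per subtype, not one in a hundred. A null subtype result could then be over-read as evidence against NIR/US. The 0.99 is the plan's only quantitative support for the subtype sizes, and a reader cannot verify it.

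**Working it through.** **Inputs from section 10.1.** Alpha 0.01; power 0.99; two-sample t-test; requirements 18, 19 and 12; 60 enrolled, about 50 completing; loss about 20%.

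**Assumptions.** Two-sided test and near-equal split, with variants below.

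**The plan's own figures.** They cannot be computed forward, because no SD is given (and no difference for ER-positive/HER2-negative). Instead I solved for the standardised difference d (mean difference divided by SD) that gives power 0.99 under each reading, and then evaluated power at the planned numbers.

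**Formula.** Power = P(T > t(1 − α/2, df)), where T is noncentral t with df = n1 + n2 − 2 and noncentrality d × √(n1 × n2 / (n1 + n2)). The opposite tail is negligible.

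**Parity.** Two groups of n total 2n, which is even. On a grid of d, a per-group size of 19 appears at d = 1.7 (total 38), while equal-group totals near 19 step 20, 18, 16.

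**Loss of 20%.** 18 × 0.8 = 14.4, taken as 7/7. 19 × 0.8 = 15.2, taken as 7/8.

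**HER2-positive and triple-negative**

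| | HER2-positive (18) | Triple-negative (19) |
|---|---|---|
| *Per-group reading:* d | 1.72 | 1.67 |
| implied SD | 25 / 1.72 = 14.5 | 34.1 / 1.67 = 20.4 |
| power, n as subtype total | 0.755 (9/9) | 0.758 (9/10) |
| power after 20% loss | 0.58 (7/7) | 0.59 (7/8) |
| *Total reading:* d | 2.59 (9/9) | 2.51 (9/10) |
| implied SD | 25 / 2.59 ≈ 9.6 | 34.1 / 2.51 = 13.6 |
| power, n as completers | 0.99 | 0.99 |
| power after 20% loss | 0.94 (7/7) | 0.95 (7/8) |

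For 9/9 the noncentrality is 1.72 × √(81/18) = 3.65, against a critical value of 2.92 on 16 df, which gives 0.755.

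**Variants, per-group reading, before loss**

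- One-sided: 0.79 for both.
- Two-sided, allowing for n having been rounded up: up to 0.79 for both. One-sided with the same allowance: up to 0.82.
- Unequal splits, two-sided: 0.73 (7/11) and 0.64 (5/13) for HER2-positive; 0.75 (8/11) and 0.68 (6/13) for triple-negative.
- Normal approximation, two-sided: 0.81.

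None comes near 0.99.

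**ER-positive/HER2-negative.** Twelve is a requirement; the planned count is whatever remains. On the per-group reading d = 2.17.

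- If ~18 and ~19 are completers, 50 − 18 − 19 = 13 remain: power 0.77 (6/7).
- If they are recruited, 60 − 18 − 19 = 23 remain: power 0.986 (11/12). After 20% loss, 23 × 0.8 = 18.4, taken as 9/9: power 0.94.

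**Enrolled or completing?** 18 + 19 + 12 = 49, close to the ~50 expected completers, which suggests that losses are already allowed for. The closing summary, however, speaks of recruiting ~18 and ~19. The text supports both readings.

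**The case against.** The strongest reply is that parity excludes 19 as a total only if the groups are equal. Responder status is observed, not assigned, and the pilot's five HER2-positive patients could not have split equally. A split of 8/11 totals 19 and gives 0.99 at d = 2.54. Section 10.1 also cites a 40% complete-response rate for triple-negative disease, close to 8/19, and 18 and 12 are both even. With the SDs missing, the per-group reading remains an inference. All of this stands. It does not settle the matter the other way, because the plan states no split. The 40% also refers to complete response (grade 5), whereas responders include grade 4.

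Three stronger readings are tempting, and the documents do not support them.

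- *Power of 0.71 for ER-positive/HER2-negative, or 0.54 after losses.* These treat 12 as the planned count. The plan assigns this subtype the remainder, about 13 completers or 23 enrolled, so neither figure should be quoted. Likewise, it is not true of all three subtypes that half the required number is planned: per group, ER-positive/HER2-negative needs 24, and as many as 23 may be enrolled.
- *The 20% loss always has to be deducted.* Because 49 is close to 50, the 18 and 19 may already be completers. The figures of 0.58 and 0.59 hold only if they are recruited numbers.
- *The trial's primary analysis is underpowered at about 0.75.* Section 10.3 plans multivariable logistic regression with ROC analysis and cross-validation. The t-test power describes only the subtype comparison used for sizing.

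**Conclusion.** The point holds as a stated power that the design probably does not deliver for the HER2-positive and triple-negative t-tests. The 0.99 is correct only if 18 and 19 are both subtype totals and completers.

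On the per-group reading, which the odd 19 makes the more natural, power is about 0.75 and 0.76, assuming a two-sided test, a near-equal split and a calculated power of exactly 0.99. Over the sidedness, rounding and split variants shown, t-based power before loss runs from about 0.64 to 0.82. On the total reading with recruited numbers the shortfall is small.

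The documents do not prove which reading is right. For ER-positive/HER2-negative the result depends on whether the remainder is 13 completers or 23 enrolled. Section 10.1 also does not make clear whether the ten exploratory endocrine patients sit inside the 60. If they do, and ~18 and ~19 are recruited numbers, 60 − 10 − 18 − 19 = 13 would be enrolled in this subtype, not 23.

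**What to change.** Check the original output. Then, in section 10.1, give for each subtype:

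- the pilot difference and pooled SD, the sidedness and the responder:non-responder split;
- whether 18, 19 and 12 are per responder group or total, and if 19 is a total, the split that produces it;
- whether ~18 and ~19 are enrolled or completing patients, the corresponding ER-positive/HER2-negative number, and whether the ten endocrine patients are counted in the 60.

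Keep enrolment as planned. Replace the stated 0.99 with the power for the expected number of completers in each subtype, and add that this is the power of the subtype t-test and not of the logistic/ROC analysis in section 10.3.

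The cost is re-reading one set of output and rewording one section. No patients or procedures are added. The downside is that the stated power may fall.

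### Section 10.1 gives 18 HER2-positive and 19 triple-negative patients both as the numbers required and as the numbers to be recruited before loss, and leaves open whether the 10 endocrine patients are within the 60

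*Combined protocol and SAP*

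**What the plan says.** All the sample size statements are in Section 10.1 of the combined protocol and SAP.

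- **Required numbers.** At alpha 0.01 and power 0.99, a two-sample t-test comparing responders with non-responders "suggests that 18 patients are required for the Her2 positive group in the new study" (change in total hemoglobin at the end of cycle 1). The corresponding calculation "suggests that 19 patients are required for the triple receptor negative group in the new study" (end of cycle 3). For ER-positive, HER2-negative disease it "suggests that 12 patients are required for this group of patient in the new study".
- **Loss.** The plan expects that "about 20% of the patients may either go to early surgery or drop the study due to side effects of treatment". It continues: "With the 60 planned patients, we expect to have approximately 50 patients who will complete the study".
- **Subtype numbers, first statement.** Directly afterwards, "we expect ~18 HER2 positive patients, ~19 triple receptor negative patients in the next two years of the award". This does not say whether the patients are enrolled or completing. The section goes on to call the numbers in these two subtypes adequate.
- **Subtype numbers, summary.** At the end of the section, "we expect to recruit ~18 HER2-positive patients, ~19 triple negative patients, and the rest may be ER-positive and HER2-negative patients".
- **Endocrine cohort.** The summary plans 10 patients for the exploratory cohort. Its next paragraph gives sixty eligible patients to be enrolled and ~50 to complete, without saying whether the 10 are among the sixty.

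**The concern.** The number a power calculation requires is the number available for the test. If 17-20% of patients are lost, the number recruited has to be larger. The summary in Section 10.1 gives the same figures for both, so a reader cannot tell whether the subtype comparisons have power 0.99 or something lower.

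The second gap concerns the total. The primary objective (Section 2) covers patients on neoadjuvant chemotherapy. If the 10 endocrine patients come out of the 60, the cohort for that objective is 50 rather than 60, and fewer chemotherapy patients complete than the three calculations add up to. Section 9 also requires the study-wide accrual target in each monitoring report, and Section 10.1 leaves that target at 60 or 70.

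**Working it through.** **Inputs (Section 10.1).** Alpha 0.01; power 0.99; required 18, 19 and 12; loss about 20%; 60 planned, ~50 completing; 10 endocrine patients. The plan does not give the SD, the sidedness of the test or the responder/non-responder split, so 18 and 19 cannot be reproduced directly. I take them as subgroup totals and back-solve.

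**Step 1: the plan's loss figure.** 60 × 0.80 = 48, against the stated ~50. Going from 60 to 50 is a loss of 1 − 50/60 = 16.7%. I use both rates below and apply them equally to each subtype, which is an assumption.

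**Step 2: completers if ~18 and ~19 are recruited.**
- HER2-positive: 18 × 0.80 = 14.4; 18 × 5/6 = 15.0.
- Triple-negative: 19 × 0.80 = 15.2; 19 × 5/6 = 15.8.

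**Step 3: power at those numbers.** I set the standardized difference d so that a two-sample t-test (noncentral t, alpha 0.01) has power 0.99 at the required total, then recompute power at the reduced numbers.

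| Subtype, test | Reference split | d | Power after loss |
|---|---|---|---|
| HER2-positive, two-sided | 9/9 | 2.594 | 7/7: 0.943; 7/8: 0.961; 8/8: 0.975 |
| HER2-positive, one-sided | 9/9 | 2.408 | 7/7: 0.950; 7/8: 0.965 |
| Triple-negative, two-sided | 9/10 | 2.510 | 7/8: 0.948; 8/8: 0.966 |
| Triple-negative, one-sided | 9/10 | 2.333 | 7/8: 0.954; 8/8: 0.969 |
| Triple-negative, two-sided, about 40/60 | 8/11 | 2.538 | 6/9: 0.945; 6/10: 0.958 |

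The last row borrows the plan's statement that "recent studies have shown that 40% of the patients achieved pathologic complete response". It is illustrative only, because responders in this trial also include Miller-Payne grade 4. The 8/8 entry for HER2-positive shows what happens if some patients who do not complete are still evaluable.

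**Step 4: the completer reading.** 18 + 19 + 12 = 49, against ~50 completing. Enrolment needed:
- At the 60-to-50 rate: 18 ÷ 5/6 = 21.6, 19 ÷ 5/6 = 22.8, 12 ÷ 5/6 = 14.4. Rounded up by subtype, 22 + 23 + 15 = 60. (Rounded once on the total, 49 ÷ 5/6 = 58.8, or 59.)
- At 20% loss: 18 ÷ 0.8 = 22.5, 19 ÷ 0.8 = 23.75, 12 ÷ 0.8 = 15.0. Rounded up, 23 + 24 + 15 = 62.

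**Step 5: the 10 endocrine patients.**

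| | Total accrual | Chemotherapy enrolled | Chemotherapy completing | Required |
|---|---|---|---|---|
| 10 inside the 60 | 60 | 50 | 50 × 0.80 = 40 to 50 × 5/6 = 41.7 | 49 |
| 10 additional | 70 | 60 | 60 × 0.80 = 48 to 60 × 5/6 = 50 | 49 |

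**The case against.** **The plan does allow for loss.** It goes from 60 planned to ~50 completing, and the next sentence gives ~18 and ~19. Since 18 + 19 + 12 = 49, those are plausibly completers. This stands as a live reading. A reader might infer that loss was forgotten or that 60 is too small; the documents do not support that. But the summary says *recruit*, which the completer reading cannot accommodate, so one statement has to change either way.

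**Not completing is not the same as not evaluable.** The sized comparisons need a scan at the end of cycle 1 or cycle 3 and a Miller-Payne grade. The expected loss includes patients who go to early surgery, and they still yield a specimen. The plan does not divide the loss by reason, timing or subtype. This also stands, for both subtypes: it would be too strong to say that power 0.99 is certainly missed, and the upper end of the range is close to 0.99.

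**The consequence is small.** Section 10.3 plans logistic regression and ROC analysis and describes no subtype t-test. I accept this, and claim no effect on that analysis.

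**The endocrine text.** A reader might infer that the statement about not immediately recruiting hormone-treated patients contradicts Sections 1.1 and 3, which include them. It does not: *not immediately* leaves room for a later exploratory cohort. Nor does it settle the total. It leans towards additional patients, whereas the summary's sixty comes straight after the 10, and its remainder group is the endocrine cohort's own phenotype. Some front matter and part of Section 1 were not in the copy read, so a total stated there cannot be excluded.

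**Conclusion.** The point holds as one of internal consistency in the stated sample size and power, and should be fixed.

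- **Power.** As the summary is worded, about 14-15 HER2-positive and 15-16 triple-negative patients complete, and power is about 0.94-0.97 instead of 0.99. This assumes that 18 and 19 are subgroup totals, that groups are near-balanced, that the loss is equal across subtypes, and that the effect sizes are those the plan's numbers imply. If patients lost after the relevant scan remain gradable, power could approach 0.99 in either subtype. If ~18 and ~19 are completers, power is as stated and the verb is wrong.
- **Accrual.** This is the more consequential part and needs no assumed SD. Either 50 chemotherapy patients enrol and about 40-42 complete, or 60 enrol and about 48-50 complete, against 49 required. The available text does not decide between them.

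**What to change.** Text changes in Section 10.1 only.

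1. In the summary, choose one reading of ~18 and ~19.
   - If they are completers, change *recruit* to *complete* and give enrolment by subtype: about 22 HER2-positive, 23 triple-negative and 15 ER-positive/HER2-negative at the 60-to-50 rate, or 23, 24 and 15 at 20% loss. Say which loss rate applies.
   - If they are recruited, replace power 0.99 with the power at the evaluable numbers, and state the SD, sidedness and responder split used.
2. State whether the 10 endocrine patients are within the 60 or additional. If within, restate the expected chemotherapy completers and the power accordingly.
3. Optionally, update the sentence on hormone-treated patients so that it reads alongside the exploratory cohort.

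The cost is a few sentences and perhaps a small table. On the first option, chemotherapy enrolment stays at 60 at the 60-to-50 rate and shows a gap of 2 (62 − 60) at 20% loss, provided the 10 are additional. On the second, the stated power becomes slightly less favourable. If the 10 prove to be inside the 60, the text will have to show the shortfall against 49.

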10.2. Primary Endpoint

The primary endpoint is pathologic response based on the Miller-Payne grading system (See Section 7 for description on grade 1~5). Patients will be grouped into responder (grade 4/5) and non-responder (grade 1~3) for statistical analysis.

10.3. Data Analysis

The multivariate logistic regression models will be used to model the binary primary endpoint. The receiver operating characteristics (ROC) curve analysis will be applied based on the fitted multivariate logistic model to evaluate the predictive ability of tumor vascularity parameters measured by NIR/US at baseline and at different treatment cycles including total, oxygenated and deoxygenated hemoglobin concentrations (abbreviated as tHb, oxyHb, deoxyHb, respectively) without and with inclusion of classic pathological variables including tumor histology, estrogen and progesterone receptor status, HER2

status, Ki67 proliferation index, Nottingham score, mitotic index, intrinsic subtype. To summarize the resulting predictive ability, the area under ROC (AUC) with DeLong's method for confidence interval calculation and the sensitivity, specificity, positive and negative predictive value corresponding to an optimal cutoff will be derived. Two models will be compared based on their AUCs based on the DeLong's method and the likelihood ratio test. To robustly assess the predictive ability, the cross validation (CV) procedure will be applied: at each CV, 2/3 of the observations will be used to train the model while the remaining will be used to validate the model.

For the exploratory neoadjuvant endocrine cohort, the analysis will also include correlation with PEPI scores.

For the additional aim, correlate tHb with enhancement on CEM.

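### Section 10.3 takes the DeLong interval, the cutoff accuracy and the DeLong model comparison from logistic models fitted in the same patients; the planned cross-validation is not made their source

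*Combined protocol and SAP*

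**What the plan says.** Section 10.3 (Data Analysis) models the binary Miller-Payne response by multivariable logistic regression and states that ROC analysis "will be applied based on the fitted multivariate logistic model to evaluate the predictive ability" of total, oxygenated and deoxygenated hemoglobin. This is done "without and with inclusion of classic pathological variables", of which eight are listed. Performance is summarised by the AUC, with DeLong's "method for confidence interval calculation and the sensitivity, specificity, positive and negative predictive value corresponding to an optimal cutoff will be derived". Next, "Two models will be compared based on their AUCs", using DeLong's method and the likelihood ratio test. A separate sentence then adds: "To robustly assess the predictive ability, the cross validation (CV) procedure will be applied", with two thirds of the observations for training and one third for validation at each round.

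Section 10 (Statistical Considerations) says that "all parameters will be inputted to the prediction model to estimate the predict power on final pathological response". It adds that, once validated on new patient data, "it can serve as a guideline for predicting patient response to neoadjuvant treatment".

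Section 10.3 does not say which AUC leads the report, how many splits are made, how their results are combined, or whether the cutoff is chosen in the training part.

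**The concern.** DeLong's variance treats the score as fixed before the data were seen. Here the score is a set of coefficients estimated from the same patients, so the apparent AUC is too high on average and its interval sits too high with it. Sensitivity, specificity, PPV and NPV at a cutoff optimised in those patients carry a second layer of optimism. For two nested fitted models, the DeLong test does not hold its nominal level.

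Cross-validation removes this optimism, but only for the quantities computed from it. A team could follow Section 10.3 to the letter, report the full-sample interval and cutoff accuracy as the result, and give a cross-validated AUC alongside. Because Section 10 intends the model as a guide for prediction, readers must be able to tell apparent from held-out performance.

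**Working it through.** **Sample size.** Section 10.1 gives 60 enrolled and about 20% loss: 60 × (1 − 0.20) = 48, against the stated figure of about 50, so the plan's number is reproduced to within 2 patients. The documents do not say whether the 10 endocrine patients are inside the 60. If they are, (60 − 10) × 0.80 = 40 chemotherapy completers.

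**Terms.** Section 10.3 lists three hemoglobin (Hb) measures. They count as two if total is taken as the sum of the other two (my assumption). The eight pathological variables are histology, ER, PR, HER2, Ki67, Nottingham score, mitotic index and intrinsic subtype. One visit per model gives 2-3 terms without pathology and 10-11 with it, or more if subtype is dummy-coded.

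**Responders.** No overall grade 4/5 rate is given, so I assume 40%, range 30-50%. At 40% of 50 there are 20 responders: 20/10 = 2.0 or 20/11 = 1.8 per term.

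**Method.** Simulated trials use unpenalised logistic fits (the plan names no penalty), independent normal predictors and the Youden cutoff. AUC is the share of responder/non-responder pairs ranked correctly. The DeLong interval is AUC ± 1.96 × SE. Optimism is apparent AUC minus the AUC of the same fitted score in new patients. Runs had 250 to 2,000 datasets per setting, and shares moved by a few percentage points between runs.

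**No signal, 50 patients, 30-50% responders**

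| Terms | Apparent AUC | DeLong lower limit > 0.5 | Held-out AUC |
|---|---|---|---|
| 2-3 (Hb only) | 0.60-0.64 | 14-32% | about 0.50 |
| 10-11 (Hb + 8 pathology) | 0.76-0.79 | 97-99% | about 0.50 |

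With 40 patients, 10-11 terms give 0.79-0.83. Using six binary and two continuous correlated pathology variables plus 2 Hb terms still gives 0.76-0.78, so the result does not hinge on independent normal predictors.

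**Cutoff accuracy, 10 noise terms, 40% responders.** Apparent sensitivity/specificity is 0.75/0.74 and PPV/NPV 0.68/0.83. Held out, with the cutoff chosen in training, they are 0.44/0.56 and 0.40/0.60.

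**Real signal**

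| Model | Apparent vs new-patient AUC | DeLong 95% coverage of new-patient AUC |
|---|---|---|
| 2-3 Hb terms, one informative (true AUC 0.75-0.85), 40% responders | optimism about 0.02-0.05 | 81-89% |
| 10 terms, two predictive pathology variables (true AUC 0.70-0.80), Hb null | 0.82-0.88 vs 0.61-0.73 | 14-24% |

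The second row matters because Section 10 itself expects pathology to predict: "high tumor grade and high proliferative activity, are associated with a better response to neoadjuvant treatment". With 4 terms (2 Hb plus the 2 predictive pathology variables), coverage is 70-77%.

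**Comparison without and with pathology, no true gain, nominal 5%.** Adding 8 null terms to 2-3 Hb terms, the DeLong test rejects in about 34-37%. In the 3 + 8 case the apparent AUC rises by 0.143 on average, against 0.00 in new patients. Adding only 2 null terms to 2 Hb terms, DeLong rejects in about 1%. The error therefore runs in either direction. The likelihood ratio test rejects in about 12-13% with 8 added terms and 6-7% with 2 added.

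**The case against.** The strongest reply is that cross-validation is planned, with an explicit train/validate split, and is introduced as the robust assessment of the same predictive ability that was just summarised. On that reading this is silence, not error. Part of this stands: the text nowhere forbids held-out values and does not contradict itself. A reader might infer that the plan has no validation, which would be wrong. But the interval, the cutoff accuracy and the comparison are tied in words to the fitted model, and nothing ties them to the splits.

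Section 10 can also be read as testing an existing pilot model in this trial's patients, which would carry no such optimism. That reading is weak, because no coefficients or cutoff are locked and Section 10.3 speaks of fitted models.

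A reader might also infer that every planned model would show an AUC near 0.77 on noise, or an interval that mostly misses the truth. Neither holds for the Hb-only models closest to the primary objective. They have 2-3 terms, and with real signal the optimism is modest.

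Finally, the likelihood ratio test is legitimately an in-sample test. Its excess rejections are small-sample error, not a consequence of missing cross-validation.

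One technical caution also stands. With 10 terms and true AUC 0.80, two-thirds training sets from 50 patients are completely separated in 24-35% of cases (1-5% under pure noise). Held-out results for large models then depend on how such fits are handled.

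**Conclusion.** The point holds and should be fixed. Followed literally, Section 10.3 reports a DeLong interval, cutoff accuracy and a DeLong comparison that do not describe performance in new patients. The harm arises if the full-sample values are the ones reported.

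Its size depends on the term count: small for a 2-3 term NIR/US model with real signal, appreciable for the same model under no signal, and severe for 10-11 terms. The likelihood ratio test is a separate and lesser matter.

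Confidence in the mechanism is high. The sizes rest on assumptions that the documents do not settle: responder rate, one visit per model, coding of the terms, predictor distribution, and 50 rather than 40 patients. The documents do not support a conclusion that the NIR/US findings as a whole would be invalid.

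**What to change.** 1. State that the headline AUC, sensitivity, specificity, PPV and NPV are held-out values averaged over repeated stratified 2/3-1/3 splits, with the cutoff and any variable selection done inside each training set. Label the full-sample AUC, DeLong interval and cutoff accuracy as apparent.
2. Attach a resampling-based interval. One option is the corrected resampled t interval, with variance equal to the variance across S splits × (1/S + n_test/n_train). In simulation it covered the new-patient AUC in 88-95% of runs, so the SAP should note that it is slightly liberal.
3. Compare models on the paired difference in held-out AUC over the same splits, in place of the DeLong test on fitted scores. Keep the likelihood ratio test for a small pre-specified model, or take its p-value by permutation.
4. State how separated training fits are handled.

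A limit on terms or a penalty is optional: it reduces optimism but restricts what one model can test. Bootstrap optimism correction is not an adequate substitute here, since it still gave about 0.59 with 10-11 noise terms (48-50 patients, 40% responders).

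The cost is SAP wording and modest programming, with no new data. Reported accuracy will be less favourable. The interval is wide, about 0.29-0.38 across at 48-50 patients. Held-out AUC is also slightly pessimistic for the final model, because each fit uses two thirds of the patients: 0.67-0.70 against 0.71-0.73 in the 10-term case with true AUC 0.80.
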